4.4 Study Outcome Measures and Ascertainment

4.4.1 Primary Outcome

- Time of admission for induction (as recorded in iCentra) to complete dilation
- Total hospital costs charged to patient, as obtained by Intermountain Healthcare billing services.

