1.2 Study Hypotheses

When compared to patients admitted to the hospital for cervical ripening:

- From the time of admission ("outpatient in a bed" status by iCentra, our EMR), patients in the outpatient cervical ripening arm will progress to complete cervical dilation in less time.
- The total overall cost of care for the encounter will be reduced for the group in the outpatient cervical ripening arm.
- Patients in the outpatient cervical ripening arm will have more overall satisfaction.

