4.2 Study Procedures

Eligible and consenting patients will be randomized by a certified research staff member using an internet based randomization system maintained by the Women and Newborn Research department. The patient will be assigned to either the inpatient or outpatient cervical ripening group. Patients will be consented and randomized at the time the patient is being scheduled for their induction. If for any reason a research staff member is unavailable to consent the patient at the time the induction is being scheduled, a time will be set for the Cervidil placement as well as a time for the induction and consent/randomization will be scheduled prior to Cervidil placement. If they are randomized to the "inpatient group" then the following induction appointment will be cancelled.

When the participant comes in for their scheduled induction, eligibility criteria will be verified again.

4.2.1 For participants randomized to the Outpatient cervical ripening arm:

- The patient will be an outpatient in L&D ("place in observation" status in iCentra) and placed on the fetal monitor. The clinician or hospitalist will perform an ultrasound for assessment of amniotic fluid volume by deepest vertical pocket (DVP) and review the fetal heart tracing. If the fetal heart rate is reactive (Category I) and the DVP is > 2cm the procedure may proceed once ordered by the attending obstetric provider or OB hospitalist.
- 2) Nursing or research staff member completes the outpatient cervical ripening case report form (CRF).
- 3) The cervix is examined and Bishop score is documented: Requirements of exam to do cervical ripening
 - a. Cervix is dilated less than 3cm
 - b. Presenting part is vertex
 - c. The provider places the Cervidil into the posterior vaginal fornix with the string at the introitus.

- d. The provider is available for immediate phone consultation by the patient or nursing staff and is readily available to L&D.
- 4) The patient is watched with continuous fetal monitoring for 2 hours.
- 5) The patient is discharged to home if all of the following are present:
 - a. Category 1 tracing X2 hours.
 - b. No vaginal bleeding
 - c. Normal maternal vital signs.
 - d. Intact BOW
 - e. Less than 1 contraction every 10 minutes at the time of discharge.

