- 6) The patient remains for further evaluation if any of the following are noted. (If the patient must remain for any of these reasons, she will need an evaluation by her attending MD or the Hospitalist prior to discharge.):
 - a. Category 2 or 3 tracing
 - b. Vaginal bleeding (beyond spotting from placement of Cervidil insert)
 - c. Any abnormal maternal vital signs (as defined in Intermountain Healthcare Standard Practice Guidelines)
 - d. ROM
 - e. More than 1 contraction every 10 minutes is noted in the last 30 minutes of monitoring.
 - f. If the insert is inadvertently dispelled from the vagina, a new insert should be placed within 15 minutes and the participant may still be discharged if she meets criteria. (The vaginal insert releases prostaglandin at a rate of 0.3 mg/hr so replacing the insert within 15 minutes will not change the overall effect of the medication)
- 7) Patient will remove the insert and return to the hospital:
 - a. For spontaneous rupture of membranes
 - b. For vaginal bleeding
 - c. Consistent contractions closer than every 10 minutes
 - d. Severe pain
 - e. Decreased fetal movement
 - f. Temperature over 100.5 degrees F.
- 8) When admitted to L&D for induction as outpatient in a bed:
 - a. Admission history and physical is done by labor nurse
 - b. Cervidil is removed and Bishop score is documented.
 - c. Results of exam are given to the attending provider.
 - d. If appropriate, Pitocin induction of labor is started per Intermountain Healthcare Standard Practice Guidelines.
- 9) Cervidil placement should not exceed 12 hours.
 - a. Management of induction per Intermountain Healthcare Standard Practice Guidelines continued at the discretion of the admitting provider.
 - b.

4.2.2 For participants randomized to the inpatient cervical ripening arm:

The patient is scheduled in L&D for:

1) Admission as "outpatient in a bed" in iCentra for hospital placement of Cervidil.

- a. The patient's priority is based on the maternal and fetal condition compared to other scheduled inductions.
- 2) Induction of labor.

Preadmission:

The patient will have education and consent to the procedure prior to admission.

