- The patient will be admitted to L&D ("outpatient in a bed" status in iCentra) and placed on the fetal monitor. The clinician or hospitalist will perform an ultrasound for assessment of amniotic fluid volume by deepest vertical pocket (DVP) and review the fetal heart tracing. If the fetal heart rate is reactive (Category I) and the DVP is > 2cm the procedure may proceed once ordered by the attending obstetric provider or OB hospitalist.
- 2) Nursing or research staff member completes the outpatient cervical ripening CRF.
- 3) If the fetal heart rate is reactive (Cat I) and the DVP is >2cm the procedure may proceed once ordered by attending obstetric provider or OB Hospitalist.
- 4) The cervix is examined: Requirements of exam to do cervical ripening
 - a. Cervix is dilated less than 3cm
 - b. Presenting part is vertex
 - c. The provider places the Cervidil into the posterior vaginal fornix with the string at the introitus.
 - d. The provider is available for immediate phone consultation by the patient or nursing staff and is readily available to L&D.
- 5) The patient is watched with continuous fetal monitoring for 2 hours.
- 6) The patient remains hospitalized
 - a. If the insert is inadvertently dispelled from the vagina, a new insert should be placed within 15 minutes and the participant may still be discharged if she meets criteria.
 (The vaginal insert releases prostaglandin at a rate of 0.3 mg/hr so replacing the insert within 15 minutes will not change the overall effect of the medication)
- 7) The Cervidil may be removed and induction of labor per Intermountain Healthcare Standard Practice Guidelines may be started per discretion of the admitting provider for any of the following:
 - a. For spontaneous rupture of membranes
 - b. For vaginal bleeding
 - c. Consistent contractions closer than every 10 minutes
 - d. Severe pain
 - e. Decreased fetal movement
 - f. Temperature over 100.5 degrees F.
 - g. Document dat/time of Cervidil removal
 - h. Document Bishop score
- 8) Cervidil placement should not exceed 12 hours.
 - a. Management of induction per Intermountain Healthcare Standard Practice Guidelines continued at the discretion of the admitting provider.

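### The primary time outcome counts cervical ripening in the inpatient arm but not for outpatients sent home, so it cannot show faster progress to complete dilation

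*Combined protocol and SAP*

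**What the plan says.** Section 1.2 states the hypothesis and names the event that starts the clock: "From the time of admission ('outpatient in a bed' status by iCentra, our EMR), patients in the outpatient cervical ripening arm" are expected to reach complete dilation sooner. Section 3.1(a) repeats the claim for the second stage of labour. Section 4.4.1 makes the interval a primary outcome: "Time of admission for induction (as recorded in iCentra) to complete dilation".

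The procedures in section 4.2 assign that status at different points in the two arms:

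- **Inpatient arm (4.2.2).** The woman is given the bed status "in iCentra for hospital placement of Cervidil". The first procedural step confirms the order: "The patient will be admitted to L&D ('outpatient in a bed' status in iCentra) and placed on the fetal monitor". Ultrasound, examination and insertion follow. Section 4.2 also cancels the separate induction appointment for this arm, so there is one admission.
- **Outpatient arm (4.2.1).** The placement visit has another status: "The patient will be an outpatient in L&D ('place in observation' status in iCentra) and placed on the fetal monitor". After insertion, "The patient is watched with continuous fetal monitoring for 2 hours". If the discharge criteria are met, she goes home. The bed status appears only at step 8, "When admitted to L&D for induction as outpatient in a bed", which is also when the insert is removed.

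Section 2.2 says that time from initiation of the method will be evaluated. Neither section 3.3 nor section 4.4 lists such an outcome.

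**The concern.** The two arms start the same clock at different stages of the same treatment. For inpatients the interval is work-up, ripening and labour to complete dilation. For outpatients sent home it is only the part after they return. Randomisation does not remove the difference, because it comes from how the outcome is defined, and section 5.3 plans nothing to correct it.

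At stake is the reading of a primary result. Sections 1.2 and 3.1(a) speak of women progressing in less time, which most readers will take to mean faster labour. A significant difference is likely even if setting has no effect on labour. A truly slower outpatient labour would still tend to be declared faster whenever the slowing falls short of the omitted time by more than the critical difference. No listed outcome has a common origin that would reveal this.

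**Working it through.** **Inputs from the protocol**
- 100 women per arm (2.2).
- Two-sample t-test at the 5% level (5.3). Sidedness is not stated; two-sided reproduces the plan's power figures.
- SD 2 h, the worked example for admission to delivery (5.1.1).
- Omitted time for a woman sent home: at least 2 h (4.2.1, step 4) and about 12 h at most (3.7.2 and 4.2.1, step 9). It is shorter for women who return early.

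**Assumptions**
- SDs of 4 and 6 h, equal SDs in the two arms, and analysis on the raw scale.
- The share of outpatients kept in hospital, and the 6 h and 3 h values in step 4.
- The inpatient work-up before placement is ignored, which understates the offset.

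**1. The plan's own figures.** With 200 per group, a two-sided t-test has 94.9% power at 0.36 SD and 79.8% at 0.28 SD, matching the stated 95% and 80%. At SD 2 h (120 min) these are 0.36 × 120 = 43.2 min and 0.28 × 120 = 33.6 min. At the 100 per arm given in 2.2, the detectable differences are 47.8 min (80% power) and 61.5 min (95% power).

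**2. No true effect, all outpatients sent home, 2 h omitted.** SE = SD × √(2/100). The critical difference is t(0.975; 198) × SE = 1.972 × SE. The probability that outpatient care is declared faster comes from the noncentral t distribution with noncentrality 2/SE.

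| SD (h) | SE (h) | Critical difference (h) | 2/SE | P(outpatient declared faster) |
|---|---|---|---|---|
| 2 | 0.283 | 0.56 | 7.07 | about 100% |
| 4 | 0.566 | 1.12 | 3.54 | 94% |
| 6 | 0.849 | 1.67 | 2.36 | 65% |

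With a common time origin and no effect, this probability would be 2.5%. The net offset that gives 80% is 0.80, 1.59 and 2.39 h at SD 2, 4 and 6 h.

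**3. Some outpatients kept after placement.** Section 4.2.1, step 6 begins "The patient remains for further evaluation if any of the following are noted" and gives no rule for when such a woman's status changes. Taking her offset as zero and the others' as 2 h (20,000 simulated trials per setting):

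| Share kept | SD 2 h | SD 4 h | SD 6 h |
|---|---|---|---|
| 20% | >99% | 79% | 47% |
| 50% | 91% | 42% | 21% |

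Repeat simulation agrees to within about one percentage point.

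**4. Outpatient labour truly slower.** Let it be 3 h slower from insertion, with a mean of 6 h omitted. The net offset is 6 − 3 = 3 h in favour of outpatients. Outpatient care is still declared faster with probability about 100%, >99% and 94% at SD 2, 4 and 6 h.

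**5. Scale.** The 2 h floor is 120/43.2 = 2.8 times and 120/33.6 = 3.6 times the differences the plan says it can detect.

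**The case against.** The strongest reply is that the clock is disclosed and prespecified. Both statements of the hypothesis begin at admission, and section 1.2 names the status. Section 2.2 presents the trial as a comparison of satisfaction and cost, where time in an admitted bed matters. On that reading a 2 h shorter interval is a real difference, and the probabilities above are power, not false-positive rates. This stands for bed use, apart from the uncounted placement visit. It does not rescue the claim of faster progress, which is what sections 1.2 and 3.1(a) word. Total time in hospital is already a separate objective, 3.1(d).

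A second reply is that admission for induction, in 4.4.1, could mean the start of induction in the inpatient arm, since 4.2.2 lists placement and induction as separate items. The single-admission reading is a choice, but the better supported one: that arm's only described admission is for placement, and its later appointment is cancelled.

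Third, the size depends on assumptions; the no-effect scenarios run from 21% to about 100%. That is fair. The documents fix the direction of the offset and its floor for women sent home, not its mean. Section 5.3 also allows a log transformation or a permutation test, so the raw-scale figures are indicative. Neither option gives the arms a common origin.

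Fourth, section 2.2 already intends a measure from initiation, and section 6.3 collects insertion time. That makes the repair easy, but the measure never reaches the outcome list.

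**Conclusion.** The concern holds and should be fixed before the outcome is used. The asymmetry follows from the protocol's own status definitions and needs no outside assumption. As defined, the primary time outcome favours outpatient care by construction and cannot support a statement about speed of labour. With no true effect and only the 2 h floor omitted, the chance of declaring outpatients faster is about 100%, 94% or 65% at SD 2, 4 or 6 h if all are sent home, falling to 91%, 42% or 21% if half are kept with no offset. These figures rest on 100 per arm, equal SDs and a two-sided 5% t-test; mean ripening time, the SD of the interval and the share kept are not in the protocol.

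A related, less certain point: under the same definition, the admission-to-discharge outcome in 4.4.2 most likely omits the outpatient placement visit, and so would favour outpatients if it is used for objective 3.1(d).

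**What to change.** - Make Cervidil insertion to complete dilation the primary time outcome in both arms, with insertion to delivery as secondary.
- State one rule, the same in both arms, for women who have a cesarean before complete dilation.
- Keep admission to complete dilation as a separately labelled bed-use outcome. Say that it excludes ripening for outpatients sent home, and state how women kept after placement are timed.
- Define total hospital time as the sum of both stays: hospital evaluation to time home, plus readmission to discharge.
- Add the times of complete dilation and discharge to the data list in 6.3. Section 3.3.1 names both as endpoints, but the list omits them.
- As a clarification only, confirm that the cost outcome includes the observation visit.

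**Cost.** Rewording in 1.2, 3.1, 3.3 and 4.4, and two added data fields; insertion, time home and readmission are already in 6.3. The test in 5.3 can stay. The power statement needs an SD for insertion to complete dilation: with 100 per arm the difference detectable at 80% power is 0.398 SD, which is 47.8 min only if that SD is 2 h. The headline difference will be smaller, because the built-in part is gone. No clinical procedure changes.

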1.1 Study Abstract

Induction of labor is a frequently planned obstetric procedure. Induction for women with an unfavorable cervix (bishop score <6) increases the risk of cesarean section. This risk may be reduced by ripening or softening the cervix before the induction of labor. This protocol outlines a randomized trial of 200 women evaluating the placement and use of Cervidil to the post vaginal fornix to soften the cervix in preparation for induction.

This trial is looking at inpatient vs outpatient pre-induction cervical ripening using Cervidil and the effects on:

- Maternal and newborn outcomes including time of admission to delivery
- System healthcare cost
- Cost to patient
- Patient satisfaction

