3.1 Primary Objectives

To show that when compared to patients admitted to the hospital for cervical ripening:

- a. From the time of admission, patients in the outpatient cervical ripening arm will progress to the second stage of labor in less time.
- b. Patients in the outpatient cervical ripening arm will have more overall satisfaction.
- c. The total overall cost of care for the encounter will be reduced for the group in the outpatient cervical ripening arm.
- d. Patients in the outpatient cervical ripening arm will spend less total time in the hospital.
- e. Cesarean section rates will be similar.

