4.4.4 Hospital System Outcomes

• Cost of hospitalization to the system

5 – STATISTICAL CONSIDERATIONS

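### Cost is scoped to one encounter or hospitalization, which read literally leaves out the outpatient arm's separate placement visit and tilts the comparison toward a saving

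*Combined protocol and SAP*

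**What the plan says.** Cost appears in three places with different scope.

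- **Section 1.2 and objective 3.1c:** "The total overall cost of care for the encounter will be reduced for the group in the outpatient cervical ripening arm". The unit is the encounter, which is not defined.
- **Section 4.4.1 (primary outcome):** "Total hospital costs charged to patient, as obtained by Intermountain Healthcare billing services". No visits, billing accounts, or start and end points are named.
- **Section 4.4.4 (hospital system outcome):** "Cost of hospitalization to the system". The unit is the hospitalization, also undefined.

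The abstract (1.1) lists "System healthcare cost" and cost to the patient as separate items. The analysis plan (5.3) gives tests for cost but no cost window, and the data elements in 6.3 include no cost field.

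The care pathways differ by arm. In 4.2.1 the outpatient-arm woman first attends L&D in observation status for monitoring, ultrasound, cervical exam and insertion. Then "The patient is watched with continuous fetal monitoring for 2 hours", and she goes home if the discharge criteria are met. Her later return is a separate step, headed "When admitted to L&D for induction as outpatient in a bed". In 4.2.2 the inpatient-arm woman is admitted once, and the same placement services fall inside that stay.

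**The concern.** A cost comparison between arms needs the same window in both. Here the planned pathway splits care into two contacts in one arm and keeps it in one contact in the other, while the objective is worded per encounter. If the analyst pulls the induction encounter or the delivery hospitalization, placement services are counted for inpatient-arm women and missed for outpatient-arm women who went home. Unscheduled returns under 4.2.1 raise the same question.

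The error would come from measurement, so randomization does not protect against it, and it runs in the direction of the hypothesis. Cost is a primary objective (3.1c) and a primary outcome (4.4.1), although the endpoint list in 3.3.1 does not include it. Section 5.3 draws conclusions from unadjusted tests at 5%.

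**Working it through.** **Step 1: which services fall in which contact.**

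| | Outpatient arm (4.2.1) | Inpatient arm (4.2.2) |
|---|---|---|
| Monitoring, ultrasound, exam, insertion, 2 h monitoring | Observation-status visit, before the induction admission | Inside the single stay |
| Induction to discharge | Later admission | Same stay |
| Counted if one encounter or hospitalization is costed | Induction to discharge only, for women who went home | Placement and induction to discharge |
| Counted if all L&D encounters are summed | Everything | Everything |

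Two further places treat the contacts as separate. Where consent is deferred, 4.2 books a placement time and an induction time, and cancels the second for women assigned to the inpatient arm. Section 6.3 records time home, time of readmission and its reason. Section 2.4.2 says that only the insert and investigator involvement are exempt from usual charges, so nothing suggests the placement visit is unbilled.

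**Step 2: size, as an illustration.** The plan gives no mean cost, cost SD or visit cost, so there is no cost figure to reproduce. Its only power statement (5.1.1) is in SD units and reproduces: 94.95% at 0.36 SD and 79.96% at 0.28 SD with 200 per group. Section 2.2 randomizes 100 per arm, so n = 100 is used here.

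Assumptions: true total cost is equal in the two arms; the visit is a share s of mean cost and is omitted for every outpatient woman; the CV is the same in both arms; the test is a two-sided 5% t-test on the raw scale (normal approximation).

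- Spurious difference in SD units: d = s / CV
- Noncentrality: δ = d / √(2/n) = d × √50 = 7.07 d
- Rejection rate: Φ(δ − 1.96) + Φ(−δ − 1.96)

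| CV | s | d | δ | Rejection rate |
|---|---|---|---|---|
| 0.4 | 5% | 0.125 | 0.88 | 14% |
| 0.4 | 10% | 0.25 | 1.77 | 42% |
| 0.8 | 5% | 0.0625 | 0.44 | 7% |
| 0.8 | 10% | 0.125 | 0.88 | 14% |

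**Step 3: partial omission.** Women who never go home may have no separate placement visit. If, say, 80% of outpatient women are affected (an assumption), d shrinks in proportion. At a CV of 0.4 it becomes 0.8 × 0.125 = 0.10 and 0.8 × 0.25 = 0.20 SD, with rejection rates of 10.9% and 29.3%.

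**Step 4: after the fix.** With all encounters summed in both arms, d = 0 and the rate returns to 5%.

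**The case against.** The strongest reply is that 4.4.1 says total, does not limit cost to an encounter or admission, and both contacts take place in the same L&D unit. On that reading nothing is omitted. This stands as a possible intention: a reader might infer that the plan will certainly leave the visit out, and the documents do not show that. They also do not say that the total spans both visits, and 1.2, 3.1c and 4.4.4 are worded more narrowly.

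Four further points have force.

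- Section 1.2 ties admission to outpatient-in-a-bed status for the time outcome, not for cost. Whether the observation visit forms its own billing account is not stated.
- It is tempting to say that every outpatient woman has two episodes. Item 6 of 4.2.1 keeps some women for further evaluation, and their placement visit may run into the induction stay.
- It is also tempting to treat patient charges and system cost as conflicting definitions of one outcome, or to conclude that charges should give way to system cost. The abstract names both perspectives, and the choice between them does not cause the asymmetry: system cost cut at admission would have the same fault. What remains open is which of the two 3.1c refers to.
- The illustrative rates depend wholly on assumed inputs, as the difference between the two CV values shows.

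**Conclusion.** The concern holds as a problem of scope. The per-encounter wording of 1.2 and 3.1c and the per-hospitalization wording of 4.4.4, applied literally to the two pathways, give cost windows that are not comparable between arms and that favour the outpatient arm. Section 4.4.1 may escape this, but it does not say so. This is more than a missing detail, because the stated unit itself creates the imbalance.

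The direction of the bias follows from the documents. Its size does not: the Step 2 rates assume the visit share, the CV and omission in every outpatient woman, and they are lower if some women are never discharged before delivery. The sponsor should settle the window before cost data are seen.

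**What to change.** In 1.2, 3.1c, 4.4.1 and 4.4.4, replace the per-encounter or per-hospitalization scope with one window: the sum over all L&D encounters from presentation for Cervidil placement to maternal discharge, including the observation visit and unscheduled returns, in both arms. Apply it to patient charges and to system cost, and state which of the two tests objective 3.1c. Patient charges need not be demoted.

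The cost is a wording change and the linking of billing encounters for each woman. It adds no patients or procedures. The apparent saving may be smaller than under a narrower window.
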